8.8.1.2 Local Tolerability Assessments

Descriptive statistics by treatment group and visit will be provided for itching, burning and stinging.

8.8.1.3 Vital Signs

Vital sign measurements include heart rate (HR), sitting blood pressure (BP) (both systolic and diastolic), body temperature, and weight. The data will be summarized with descriptive statistics by visit and treatment group. In addition, the changes from baseline will be summarized with descriptive statistics.

Furthermore, to identify potentially clinically significant vital signs, the following criteria will be used and tabulated as a shift table by visit:

- Systolic Blood Pressure: <90 mmHg (low), 90-140 mmHg (normal), >140 mmHg (high)

- Diastolic Blood Pressure: <90 mm Hg (low), 90-100 mmHg (normal), >100 mmHg (high)

Heart Rate: <60 beats per minute (low), 60-100 beats per minute (normal), >100 beats per minute (high).

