17.6.1 Vital Sign Measurements

Vital signs as well as changes from Baseline in vital sign measurements will be summarized with descriptive statistics for each treatment group at all applicable study visits.

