8.1.6 Interim Analyses and Data Monitoring

No interim analysis or data monitoring is planned for this study.

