8.4.3 Safety Population

All subjects in the randomized population who are presumed to have used the study product at least once and who provide at least one post-baseline safety evaluation will be included in the Safety population and will be analyzed according to the treatment they received. Presumed to have used study product will be defined as having at least one confirmed application of study medication. All safety analyses will be performed using the Safety population.

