Min. to Max.	xx to xx	xx to xx
Change from Baseline		
n	xxx	xxx
Mean	xx.x	xx.x
SD	xx.xx	xx.xx
Median	xx.x	xx.x
Min. to Max.	xx to xx	xx to xx

Note: No imputation of missing values. Negative change values represent decrease from Baseline.

SOURCE: USERNAME\SPONSOR\PROJECT\JOBNAME (DATE, TIME)

Table 14.3.1.4: Summary of Vital Signs
(Safety Population)
(Page 3 of 5)

Systolic Blood Pressure (mmHg)	E-BPO/E-ATRA 3%/0.1% Cream (N=xxx)	Vehicle Cream (N=xxx)
Baseline		
n	xxx	xxx
Mean	xx.x	xx.x
SD	xx.xx	xx.xx
Median	xx.x	xx.x
Min. to Max.	xx to xx	xx to xx
Week 12		
n	xxx	xxx
Mean	xx.x	xx.x
SD	xx.xx	xx.xx
Median	xx.x	xx.x
Min. to Max.	xx to xx	xx to xx
Change from Baseline		
n	xxx	xxx
Mean	xx.x	xx.x
SD	xx.xx	xx.xx
Median	xx.x	xx.x
Min. to Max.	xx to xx	xx to xx

Note: No imputation of missing values. Negative change values represent decrease from Baseline.

SOURCE: USERNAME\SPONSOR\PROJECT\JOBNAME (DATE, TIME)

Table 14.3.1.4: Summary of Vital Signs
(Safety Population)
(Page 4 of 5)

Diastolic Blood Pressure (mmHg)	E-BPO/E-ATRA 3%/0.1% Cream (N=xxx)	Vehicle Cream (N=xxx)
Baseline		
n	xxx	xxx
Mean	xx.x	xx.x
SD	xx.xx	xx.xx
Median	xx.x	xx.x
Min. to Max.	xx to xx	xx to xx
Week 12		
n	xxx	xxx
Mean	xx.x	xx.x
SD	xx.xx	xx.xx
Median	xx.x	xx.x
Min. to Max.	xx to xx	xx to xx
Change from Baseline		
n	xxx	xxx
Mean	xx.x	xx.x
SD	xx.xx	xx.xx
Median	xx.x	xx.x
Min. to Max.	xx to xx	xx to xx

Note: No imputation of missing values. Negative change values represent decrease from Baseline.

SOURCE: USERNAME\SPONSOR\PROJECT\JOBNAME (DATE, TIME)

Table 14.3.1.4: Summary of Vital Signs
(Safety Population)
(Page 5 of 5)

Heart Rate (beats/min)	E-BPO/E-ATRA 3%/0.1% Cream (N=xxx)	Vehicle Cream (N=xxx)
Baseline		
n	xxx	xxx
Mean	xx.x	xx.x
SD	xx.xx	xx.xx
Median	xx.x	xx.x
Min. to Max.	xx to xx	xx to xx
Week 12		
n	xxx	xxx
Mean	xx.x	xx.x
SD	xx.xx	xx.xx
Median	xx.x	xx.x
Min. to Max.	xx to xx	xx to xx
Change from Baseline		
n	xxx	xxx
Mean	xx.x	xx.x
SD	xx.xx	xx.xx
Median	xx.x	xx.x
Min. to Max.	xx to xx	xx to xx

Note: No imputation of missing values. Negative change values represent decrease from Baseline.

SOURCE: USERNAME\SPONSOR\PROJECT\JOBNAME (DATE, TIME)

Table 14.3.1.4.2: Shift Table of Vital Signs
(Safety Population)

	E-BPO/E-ATRA 3%/0.1% Cream (N=xxx)			Vehicle Cream (N=xxx)		
Systolic Blood Pressure (mmHg)	Week 12			Week 12		
Baseline	<90 mmHg	90-140 mmHg	>140 mmHg	<90 mmHg	90-140 mmHg	>140 mmHg

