<90 mmHg	xx (xx.x%)	xx (xx.x%)	xx (xx.x%)	xx (xx.x%)	xx (xx.x%)	xx (xx.x%)
90-140 mmHg	xx (xx.x%)	xx (xx.x%)	xx (xx.x%)	xx (xx.x%)	xx (xx.x%)	xx (xx.x%)
>140 mmHg	xx (xx.x%)	xx (xx.x%)	xx (xx.x%)	xx (xx.x%)	xx (xx.x%)	xx (xx.x%)
Diastolic Blood Pressure (mmHg)	Week 12			Week 12		
Baseline	<90 mmHg	90-100 mmHg	>100 mmHg	<90 mmHg	90-100 mmHg	>100 mmHg
<90 mmHg	xx (xx.x%)	xx (xx.x%)	xx (xx.x%)	xx (xx.x%)	xx (xx.x%)	xx (xx.x%)
90-100 mmHg	xx (xx.x%)	xx (xx.x%)	xx (xx.x%)	xx (xx.x%)	xx (xx.x%)	xx (xx.x%)
>100 mmHg	xx (xx.x%)	xx (xx.x%)	xx (xx.x%)	xx (xx.x%)	xx (xx.x%)	xx (xx.x%)
Heart Rate (beats/min)	Week 12			Week 12		
Baseline	<60 bpm	60-100 bpm	>100 bpm	<60 bpm	60-100 bpm	>100 bpm
<60 mmHg	xx (xx.x%)	xx (xx.x%)	xx (xx.x%)	xx (xx.x%)	xx (xx.x%)	xx (xx.x%)
60-100 mmHg	xx (xx.x%)	xx (xx.x%)	xx (xx.x%)	xx (xx.x%)	xx (xx.x%)	xx (xx.x%)
>100 mmHg	xx (xx.x%)	xx (xx.x%)	xx (xx.x%)	xx (xx.x%)	xx (xx.x%)	xx (xx.x%)

Note: No imputation of missing values.

SOURCE: USERNAME\SPONSOR\PROJECT\JOBNAME (DATE, TIME)

Table 14.3.1.5: Summary of Abnormal Physical Examination Findings by Visit
(Safety Population)

	E-BPO 3% Cream (N=xxx)	Vehicle Cream (N=xxx)
Heart		
Baseline		
n	xx	xx
Abnormal	xx (xx.x%)	xx (xx.x%)
Week 12		
n	xx	xx
Abnormal	xx (xx.x%)	xx (xx.x%)
Lung		
Baseline		
n	xx	xx
Abnormal	xx (xx.x%)	xx (xx.x%)
Week 12		
n	xx	xx
Abnormal	xx (xx.x%)	xx (xx.x%)
Abdomen		
Baseline		
n	xx	xx
Abnormal	xx (xx.x%)	xx (xx.x%)
Week 12		
n	xx	xx
Abnormal	xx (xx.x%)	xx (xx.x%)

Note: No imputation of missing values.

SOURCE: USERNAME\SPONSOR\PROJECT\JOBNAME (DATE, TIME)

Table 14.3.1.6: Summary of Patient Global Impression of Treatment Side-Effects (PGI-SE) at Each Evaluation
(Safety Population)
(Page 1 of 2)

Right now, how bothered are you by the side effects of your acne treatment:	E-BPO/E-ATRA 3%/0.1% Cream (N=xxx)	Vehicle Cream (N=xxx)
Week 2		
n	xx	xx
0 - I am not bothered	xx (xx.x%)	xx (xx.x%)
1 - I am somewhat bothered	xx (xx.x%)	xx (xx.x%)
2 - I am moderately bothered	xx (xx.x%)	xx (xx.x%)
3 - I am very bothered	xx (xx.x%)	xx (xx.x%)
4 - I am extremely bothered	xx (xx.x%)	xx (xx.x%)
Week 4		
n	xx	xx
0 - I am not bothered	xx (xx.x%)	xx (xx.x%)
1 - I am somewhat bothered	xx (xx.x%)	xx (xx.x%)
2 - I am moderately bothered	xx (xx.x%)	xx (xx.x%)
3 - I am very bothered	xx (xx.x%)	xx (xx.x%)
4 - I am extremely bothered	xx (xx.x%)	xx (xx.x%)
Week 8		
n	xx	xx

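### The SAP's diastolic categories start at 90 mmHg, the same lower limit as systolic, so the diastolic shift table calls everything below 90 low and cannot show a fall within that range

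*SAP*

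**What the plan says.** SAP section 8.8.1.3 introduces a set of categories whose purpose is "to identify potentially clinically significant vital signs", to be tabulated as shifts. For systolic pressure it gives "Systolic Blood Pressure: <90 mmHg (low), 90-140 mmHg (normal), >140 mmHg (high"; for diastolic pressure, "Diastolic Blood Pressure: <90 mm Hg (low), 90-100 mmHg (normal), >100 mmHg (high".

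The matching shell, "Table 14.3.1.4.2: Shift Table of Vital Signs", crosses Baseline with Week 12 and uses the diastolic bands <90, 90-100 and >100 mmHg. It prints the numbers only, without the words low, normal or high. Its footnote reads "Note: No imputation of missing values".

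Nothing elsewhere replaces these bands. Protocol section 17.6.1 has no categories; it says only that vital signs and "changes from Baseline in vital sign measurements will be summarized with descriptive statistics". SAP section 10, which lists departures from the protocol, does not mention them.

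**The concern.** The two pressures share a lower limit of 90 mmHg, although diastolic pressure is below systolic in any reading. The diastolic labels therefore look misplaced: an ordinary-looking reading is coded low, and a rise can be coded as a return to normal.

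At stake is whether the diastolic block can do the job the SAP gives it. A table meant to pick out notable values needs a lower cut that separates some low readings from the rest. Here the only cuts are at 90 and 100, so a fall that starts and ends below 90 does not appear as a shift, however large it is.

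**Working it through.** No sample size, power or alpha is involved, so there is no planned figure to reproduce. The check compares the text with the shell, applies the SAP's rule to example values, and then gauges how many patients the lowest band would hold.

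**1. Text against shell.**

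| Measure | Low | Normal | High | Width of normal band |
|---|---|---|---|---|
| Systolic, SAP 8.8.1.3 | <90 | 90-140 | >140 | 140 − 90 = 50 mmHg |
| Diastolic, SAP 8.8.1.3 | <90 | 90-100 | >100 | 100 − 90 = 10 mmHg |
| Diastolic, Table 14.3.1.4.2 shell | <90 | 90-100 | >100 (no labels printed) | 10 mmHg |

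Text and shell agree, so this is not a slip confined to one place. The two pressures are classified separately and every reading can be coded, so there is no logical contradiction. The difficulty lies in what the diastolic labels mean.

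**2. Labels, using only the fact that diastolic is below systolic.** A patient at systolic 90, the SAP's own lower edge of normal, must be coded diastolic low. To be normal on both pressures, a patient needs a diastolic value of 90-100 with a systolic value above it and no higher than 140.

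**3. The rule applied to Baseline and Week 12 pairs.**

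| Baseline → Week 12 diastolic (mmHg) | Coded as |
|---|---|
| 89 → 50 | low → low |
| 85 → 60 | low → low |
| 70 → 45 | low → low |
| 60 → 89 (a rise) | low → low |
| 80 → 95 (a rise) | low → normal |
| 95 → 85 | normal → low |
| 95 → 60 | normal → low |

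All integer pairs with both values from 30 to 89 fall in the single low → low cell. A fall shows only if it crosses 90 or 100, and falls from 95 to 85 and from 95 to 60 cannot be told apart. This step needs no distributional assumption.

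**4. How full that cell would be.** The documents give no diastolic mean, SD or between-visit correlation, so these are assumptions. With a normal distribution at each visit (mean μ, SD σ), the share of single readings below 90 is Φ((90 − μ)/σ). The share below 90 at both visits is the bivariate normal probability with both limits at (90 − μ)/σ and correlation ρ; at ρ = 0 it is the square of the single-reading share.

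- μ = 65, σ = 8: Φ(3.125) = 0.9991; both visits 0.9982 (ρ = 0) to 0.9984 (ρ = 0.7).
- μ = 75, σ = 10: Φ(1.5) = 0.9332; both visits 0.8708 to 0.8946.
- μ = 80, σ = 12: Φ(0.833) = 0.7977; both visits 0.6363 to 0.7099.
- μ = 85, σ = 8 to 12, a deliberately high mean: single readings 0.7340 down to 0.6615; both visits 0.4376 to 0.6310 over both σ and ρ.

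For means of 65-80 and SDs of 8-12, about 80-99.9% of single readings and 64-99.8% of patients fall below 90. At a mean of 85 the figures are 66-73% and 44-63%. The denominator is patients in the Safety population with both a Baseline and a Week 12 value. That population requires only a post-baseline safety evaluation of some kind ("at least one post-baseline safety evaluation will be included in the Safety population") and nothing is imputed, so the number is not known in advance and only percentages are given.

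**The case against.** Any three-band shift table hides changes within a band. By the SAP's systolic limits a fall from 140 to 91 mmHg is normal to normal and equally invisible. That is true, and hiding within-band change is not in itself a diastolic defect. What is particular to diastolic is that the band likely to hold most readings is also the lowest one, open-ended below and labelled low. The systolic scheme at least has a low band set apart from a wide normal one.

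The documents contain no diastolic reference range, so calling the labels implausible draws partly on general knowledge. That the systolic limit was copied across is an inference: the documents show that the limits are equal, not why. Both points are fair. The single-cell result needs neither of them.

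The percentages rest on assumed inputs and span a wide range. They indicate scale and are not estimates for this trial.

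The practical effect is small. Table 14.3.1.4 still gives the diastolic mean, SD, median, range and change from Baseline, and Listing 16.2.8.3 gives every value. SAP section 7.2 lists vital signs among the safety assessments, but the protocol's safety endpoints are adverse events and cutaneous and local tolerability. No test uses the bands, and they feed no ongoing review ("No interim analysis or data monitoring is planned for this study"). All of this stands and limits the weight of the point.

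**Conclusion.** The concern holds, as a minor one. As written, the diastolic block labels every reading below 90 mmHg low and puts every patient below 90 at both visits in one cell, so it cannot show a diastolic fall within that range. Falls from 90 or above to below 90, and rises across 90 or 100, are still shown. That conclusion follows from the bands alone. The share of patients affected, about 64-99.8% (44-63% at the higher assumed mean of 85), depends on the assumed normal distribution, means, SDs and correlations. The damage is confined to one descriptive table that the SAP adds to the protocol's plan. Efficacy, type I error and sample size are untouched.

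**What to change.** Before unblinding, have the sponsor's medical reviewer review and correct the diastolic categories, or record the reason if the present ones are intended. Then change the line in SAP section 8.8.1.3 and the diastolic block of the Table 14.3.1.4.2 shell together, since they currently carry the same bands. No specific limits are proposed here.

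Separately, the heart-rate rows of that shell are labelled mmHg while the columns read bpm. This unrelated slip can be corrected in the same edit.

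The cost is one line of SAP text and one table shell, with no effect on data collection, patients or sample size.

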8.8.1.4 Physical Examination

Abnormal physical examination findings will be summarized by body system, visit, and treatment group. In addition to the summary, all physical examination findings will be listed.

9. DETERMINATION OF SAMPLE SIZE

The following power calculations are based on the observed Week 12 results of the Phase 2 study, SGT-65-02. This study was a six-arm trial including S6G5T-3 and Vehicle Cream in the treatment of acne vulgaris. Estimates from the S6G5T-3 arm were used in the power assessments. The anticipated randomization ratio is 2:1 for S6G5T-3 and S6G5T-8 Vehicle Cream, respectively. The computations were performed with nQuery Advisor Version 7.0 using a two-sided test with a statistical significance value of 0.05.

A sample size of 274 in the S6G5T-3 and 137 in the Vehicle Cream group (total of 411) has 99% power to detect a statistically significant difference in inflammatory lesions. The estimated absolute change from Baseline in treatment means were -16.7 and -12.2 for S6G5T-3 and Vehicle Cream, respectively, with a common standard deviation of 10.0.

A sample size of 146 in the S6G5T-3 and 73 in the Vehicle Cream group (total of 219) has 99% power to detect a statistically significant difference in non-inflammatory lesions. The estimated absolute change from Baseline in treatment means were -23.7 and -13.7 for S6G5T-3 and Vehicle Cream, respectively, with a common standard deviation of 19.0.

A sample size of 231 in the S6G5T-3 and 116 in the Vehicle Cream has group (total of 346) has 99% power to detect a statistically significant difference the proportion of Patients who have at least a 2-grade reduction at Week 12 from Baseline in IGA and are Clear or Almost Clear. The estimated percentages with a 2-grade reduction at Week 12 from Baseline in the IGA and Clear or Almost Clear are 33.3% and 12.6% for S6G5T-3 and Vehicle Cream, respectively.

Therefore, a total of 420 Patients has adequate power to demonstrate statistical significance of S6GT5-3 over S6GT5-8 Vehicle Cream for the lesion count endpoints as well as dichotomized IGA.

10. CHANGES IN THE PLANNED ANALYSES

There are no changes in the conduct of the study, but there are minor changes to the planned analyses.

Absolute change from Baseline in inflammatory and non-inflammatory lesion counts from Baseline to weeks 4 and 8 were removed from the supportive efficacy endpoints, as they were also included in the secondary efficacy endpoints.

The pooling analysis described in the protocol is updated in the statistical analysis plan (SAP) to reflect the intended analysis. The protocol discusses pooling sites with five or fewer subjects enrolled in each treatment arm. Taking into consideration the randomization ratio, the SAP requires ten subjects in the active treatment arm and five subjects in the vehicle group.

As part of the pooling analysis, the treatment effect within investigational site must be investigated. The protocol states the site main effect will be examined by using a one-way analysis of variance (for lesion count variables) or a logistic regression analysis (for dichotomized IGA) with a factor of site. The SAP instead explains site will be incorporated into the primary analysis models. Change from Baseline in lesion counts will be analyzed with an ANCOVA (unranked or ranked) with factors of treatment group, investigational site and treatment group by investigational site interaction, and the respective Baseline lesion count variable as a covariate. The dichotomized primary endpoint will be analyzed with a logistic regression with factors of treatment group, investigational site and the interaction term of treatment group by investigational site.

The protocol describes repeated measures sensitivity analyses for the primary efficacy endpoints. Treatment group, analysis center and visit are listed as factors for the repeated measures analyses. In addition to these factors, the SAP includes a factor of treatment group by visit interaction.

The protocol describes imputing only Week 12 data with MCMC imputation, but all missing post-Baseline data will be imputed. The protocol provided did not provide seeds for the IGA MCMC imputation or for the model based multiple imputation, so those were added in the SAP.

Geographic region was removed from the examination of subgroups as all sites in the study are in the United States.

An additional age grouping of 9-11 years, 12-17 years, 18-30 years, and 31 years and older was added to the subgroup summaries.

The secondary efficacy analysis will be presented on the PP population in addition to the ITT population as specified in the protocol.

Table 14.3.1.2.1: Summary of Treatment-Emergent Adverse Event Characteristics (Safety Population).....	152
Table 14.3.1.2.2: Summary of Treatment-Emergent Adverse Events by MedDRA System Organ Class and Preferred Term (Safety Population).....	154
Table 14.3.1.2.3: Summary of Treatment-Emergent Adverse Events by Severity (Safety Population)	155
Table 14.3.1.2.4: Summary of Treatment-Emergent Adverse Events by Relationship to Study Drug (Safety Population)	156
Table 14.3.1.3.1: Summary of Treatment-Emergent Serious Adverse Event Characteristics (Safety Population).....	157
Table 14.3.1.3.2: Summary of Treatment-Emergent Serious Adverse Events by MedDRA System Organ Class and Preferred Term (Safety Population).....	159
Table 14.3.1.3.3: Summary of Serious Treatment-Emergent Adverse Events by Severity (Safety Population)	160
Table 14.3.1.3.4: Summary of Treatment-Emergent Serious Adverse Events by Relationship to Study Drug (Safety Population).....	161
Table 14.3.1.4: Summary of Vital Signs (Safety Population)	162
Table 14.3.1.4.2: Shift Table of Vital Signs (Safety Population).....	167
Table 14.3.1.5: Summary of Abnormal Physical Examination Findings by Visit (Safety Population)	168
Table 14.3.1.6: Summary of Patient Global Impression of Treatment Side-Effects (PGI-SE) at Each Evaluation (Safety Population).....	169

Table 14.0.1: Summary of Subject Completion/Discontinuation
(All Randomized Subjects)

	E-BPO/E-ATRA 3%/0.1% Cream (N= xxx)	Vehicle Cream (N=xxx)	Total (N=xxx)
Completed Study			
Yes	xx (xx.x%)	xx (xx.x%)	xx (xx.x%)
No	xx (xx.x%)	xx (xx.x%)	xx (xx.x%)
Reason for Discontinuation			
Adverse Event	xx (xx.x%)	xx (xx.x%)	xx (xx.x%)
Lost to Follow-Up	xx (xx.x%)	xx (xx.x%)	xx (xx.x%)
Lack of Efficacy	xx (xx.x%)	xx (xx.x%)	xx (xx.x%)
Pregnancy	xx (xx.x%)	xx (xx.x%)	xx (xx.x%)
Protocol Violation	xx (xx.x%)	xx (xx.x%)	xx (xx.x%)
Withdrawal by Parent/Guardian	xx (xx.x%)	xx (xx.x%)	xx (xx.x%)
Withdrawal by Subject	xx (xx.x%)	xx (xx.x%)	xx (xx.x%)
Study Terminated by Sponsor	xx (xx.x%)	xx (xx.x%)	xx (xx.x%)
Physician Decision	xx (xx.x%)	xx (xx.x%)	xx (xx.x%)
Worsening of Condition	xx (xx.x%)	xx (xx.x%)	xx (xx.x%)
Other	xx (xx.x%)	xx (xx.x%)	xx (xx.x%)

SOURCE: USERNAME\SPONSOR\PROJECT\JOBNAME (DATE, TIME)

Table 14.0.2.1: Summary of Subject Enrollment and Evaluability
(All Randomized Subjects)

	E-BPO/E-ATRA 3%/0.1% Cream (N=xxx)	Vehicle Cream (N=xxx)	Total (N=xxx)
Number of Randomized Subjects	xx	xx	xx
Number of Subjects Included in the ITT Population	xx (xx.x%)	xx (xx.x%)	xx (xx.x%)
Number of Subjects Excluded from the ITT Population	xx (xx.x%)	xx (xx.x%)	xx (xx.x%)
Reason Excluded from the ITT Population			
Not Dispensed Study Drug	xx (xx.x%)	xx (xx.x%)	xx (xx.x%)
Number of Subjects Included in the Safety Population	xx (xx.x%)	xx (xx.x%)	xx (xx.x%)
Number of Subjects Excluded from the Safety Population	xx (xx.x%)	xx (xx.x%)	xx (xx.x%)
Reasons Excluded from the Safety Population ^a			
No Documented use of Study Drug	xx (xx.x%)	xx (xx.x%)	xx (xx.x%)
No Post-Baseline Safety Assessment	xx (xx.x%)	xx (xx.x%)	xx (xx.x%)
Number of Subjects Included in the PP Population	xx (xx.x%)	xx (xx.x%)	xx (xx.x%)
Number of Subjects Excluded from the PP Population	xx (xx.x%)	xx (xx.x%)	xx (xx.x%)
Reasons Excluded from the PP Population ^a			
Not Included in ITT Population	xx (xx.x%)	xx (xx.x%)	xx (xx.x%)
Violated Inclusion/Exclusion Criteria	xx (xx.x%)	xx (xx.x%)	xx (xx.x%)
Used Interfering Concomitant Medication	xx (xx.x%)	xx (xx.x%)	xx (xx.x%)
Did not Attend Week 12/ET Visit	xx (xx.x%)	xx (xx.x%)	xx (xx.x%)
Missed More Than 1 Post-Baseline Visit Prior to Week 12	xx (xx.x%)	xx (xx.x%)	xx (xx.x%)
Not Compliant with Dosing Regimen ^b	xx (xx.x%)	xx (xx.x%)	xx (xx.x%)
Week 12/ET Visit Out of Window (+/-4 days)	xx (xx.x%)	xx (xx.x%)	xx (xx.x%)
Other	xx (xx.x%)	xx (xx.x%)	xx (xx.x%)

^a Table includes primary reason (assigned in order presented in table) for reason subject was excluded.

^b Subjects lost to follow-up not included. A subject was considered compliant with the dosing regimen if the subject applied 80-120% of the expected number of applications and did not miss more than 5 consecutive applications while enrolled in the study.

SOURCE: USERNAME\SPONSOR\PROJECT\JOBNAME (DATE,TIME)

Table 14.0.2.2: Summary of Subject Evaluability by Analysis Center and Investigational Site
 (All Randomized Subjects)
 (Page 1 of xx)

Analysis Center	Investigational Site	Number Randomized	E-BPO/E-ATRA 3%/0.1% Cream			Vehicle Cream		
			ITT	PP	Safety	ITT	PP	Safety
xx	xx	xx	xx	xx	xx	xx	xx	xx
xx	xx	xx	xx	xx	xx	xx	xx	xx
	xx	xx	xx	xx	xx	xx	xx	xx
xx	xx	xx	xx	xx	xx	xx	xx	xx
xx	xx	xx	xx	xx	xx	xx	xx	xx
	xx	xx	xx	xx	xx	xx	xx	xx
	xx	xx	xx	xx	xx	xx	xx	xx

SOURCE: USERNAME\SPONSOR\PROJECT\JOBNAME (DATE,TIME)

Table 14.1.1.1: Summary of Subject Demographic Characteristics
(Intent-to-Treat Population)
(Page 1 of 2)

	E-BPO/E-ATRA 3%/0.1% Cream (N=xxx)	Vehicle Cream (N=xxx)	Total (N=xxx)	P-Value
Age (years)				
n	xx	xx	xx	x.xxx ^a
Mean	xx.x	xx.x	xx.x	
SD	xx.xx	xx.xx	xx.xx	
Median	xx.x	xx.x	xx.x	
Min. to Max.	xx to xx	xx to xx	xx to xx	
< Median (xx years)	xx (xx.x%)	xx (xx.x%)	xx (xx.x%)	
≥ Median (xx years)	xx (xx.x%)	xx (xx.x%)	xx (xx.x%)	
< 18 years	xx (xx.x%)	xx (xx.x%)	xx (xx.x%)	
≥ 18 years and < Median (xx years)	xx (xx.x%)	xx (xx.x%)	xx (xx.x%)	
≥ Median (xx years)	xx (xx.x%)	xx (xx.x%)	xx (xx.x%)	
9-11 years	xx (xx.x%)	xx (xx.x%)	xx (xx.x%)	
12-17 years	xx (xx.x%)	xx (xx.x%)	xx (xx.x%)	
18-30 years	xx (xx.x%)	xx (xx.x%)	xx (xx.x%)	
≥ 31 years	xx (xx.x%)	xx (xx.x%)	xx (xx.x%)	

^a P-value from a two-way analysis of variance with factors of treatment group and analysis center.

^b P-value from a Cochran-Mantel-Haenszel general association test, stratified by analysis center.

^c See Listing 16.2.4.1 for a complete list of other races.

SOURCE: USERNAME\SPONSOR\PROJECT\JOBNAME (DATE,TIME)

Table 14.1.1.1: Summary of Subject Demographics
(Intent-to-Treat Population)
(Page 2 of 2)

	E-BPO/E-ATRA 3%/0.1% Cream (N=xxx)	Vehicle Cream (N=xxx)	Total (N=xxx)	P-Value
Sex				
n	xx	xx	xx	x.xxx ^b
Male	xx (xx.x%)	xx (xx.x%)	xx (xx.x%)	
Female	xx (xx.x%)	xx (xx.x%)	xx (xx.x%)	
Ethnicity				
n	xx	xx	xx	x.xxx ^b
Hispanic or Latino	xx (xx.x%)	xx (xx.x%)	xx (xx.x%)	
Not Hispanic or Latino	xx (xx.x%)	xx (xx.x%)	xx (xx.x%)	
Race				
n	xx	xx	xx	x.xxx ^b
American Indian or Alaska Native	xx (xx.x%)	xx (xx.x%)	xx (xx.x%)	
Asian	xx (xx.x%)	xx (xx.x%)	xx (xx.x%)	
Black or African American	xx (xx.x%)	xx (xx.x%)	xx (xx.x%)	
Native Hawaiian or Other Pacific Islander	xx (xx.x%)	xx (xx.x%)	xx (xx.x%)	
White	xx (xx.x%)	xx (xx.x%)	xx (xx.x%)	
Multiple/Other ^c	xx (xx.x%)	xx (xx.x%)	xx (xx.x%)	

^a P-value from a two-way analysis of variance with factors of treatment group and analysis center.

^b P-value from a Cochran-Mantel-Haenszel general association test, stratified by analysis center.

^c See Listing 16.2.4.1 for a complete list of other races.

SOURCE: USERNAME\SPONSOR\PROJECT\JOBNAME (DATE,TIME)

Repeat Table 14.1.1.1 for the following tables:

Table 14.1.1.2: Summary of Subject Demographics (Per-Protocol Population)

Table 14.1.1.3: Summary of Subject Demographics (Safety Population)

Table 14.1.2.1: Subject Baseline Characteristics
(Intent-to-Treat Population)
(Page 1 of 2)

	E-BPO/E-ATRA 3%/0.1% Cream (N=xxx)	Vehicle Cream (N=xxx)	Total (N=xxx)	P-Value
Height (cm)				
n	xx	xx	xx	x.xxx ^a
Mean	xx.x	xx.x	xx.x	
SD	xx.xx	xx.xx	xx.xx	
Median	xx.x	xx.x	xx.x	
Min. to Max.	xx to xx	xx to xx	xx to xx	
Weight (kg)				
n	xx	xx	xx	x.xxx ^a
Mean	xx.x	xx.x	xx.x	
SD	xx.xx	xx.xx	xx.xx	
Median	xx.x	xx.x	xx.x	
Min. to Max.	xx to xx	xx to xx	xx to xx	
BMI (kg/m²)				
n	xx	xx	xx	x.xxx ^a
Mean	xx.x	xx.x	xx.x	
SD	xx.xx	xx.xx	xx.xx	
Median	xx.x	xx.x	xx.x	
Min. to Max.	xx to xx	xx to xx	xx to xx	

^a P-value from a two-way analysis of variance with factors of treatment group and analysis center.

^b P-value from a Cochran-Mantel-Haenszel general association test, stratified by analysis center.

SOURCE: USERNAME\SPONSOR\PROJECT\JOBNAME (DATE,TIME)

Table 14.1.2.1: Subject Baseline Characteristics
(Intent-to-Treat Population)
(Page 2 of 2)

	E-BPO/E-ATRA 3%/0.1% Cream (N=xxx)	Vehicle Cream (N=xxx)	Total (N=xxx)	P-Value
Inflammatory Lesion Count				
n	xx	xx	xx	x.xxx ^a
Mean	xx.x	xx.x	xx.x	
SD	xx.xx	xx.xx	xx.xx	
Median	xx.x	xx.x	xx.x	
Min. to Max.	xx to xx	xx to xx	xx to xx	
Non-Inflammatory Lesion Count				
n	xx	xx	xx	x.xxx ^a
Mean	xx.x	xx.x	xx.x	
SD	xx.xx	xx.xx	xx.xx	
Median	xx.x	xx.x	xx.x	
Min. to Max.	xx to xx	xx to xx	xx to xx	
Investigator Global Assessment				
n	xx	xx	xx	x.xxx ^b
0 - Clear	xx (xx.x%)	xx (xx.x%)	xx (xx.x%)	
1 - Almost Clear	xx (xx.x%)	xx (xx.x%)	xx (xx.x%)	
2 - Mild	xx (xx.x%)	xx (xx.x%)	xx (xx.x%)	
3 - Moderate	xx (xx.x%)	xx (xx.x%)	xx (xx.x%)	
4 - Severe	xx (xx.x%)	xx (xx.x%)	xx (xx.x%)	

^a P-value from a two-way analysis of variance with factors of treatment group and analysis center.

^b P-value from a Cochran-Mantel-Haenszel general association test, stratified by analysis center.

SOURCE: USERNAME\SPONSOR\PROJECT\JOBNAME (DATE,TIME)

Repeat Table 14.1.2.1 for the following table:

Table 14.1.2.2: Subject Baseline Characteristics (Per-Protocol Population)

Table 14.1.2.3: Subject Baseline Characteristics (Safety Population)

Table 14.1.3.1: Summary of Medical History by System Organ Class and Preferred Term
 (Intent-to-Treat Population)
 (Page 1 of xx)

System Organ Class Preferred Term	E-BPO/E-ATRA 3%/0.1% Cream (N=xxx)		Vehicle Cream (N=xxx)		Total (N=xxx)	
	By Subject ^a	By Event ^b	By Subject ^a	By Event ^b	By Subject ^a	By Event ^b
Number (%) of Subjects Reporting at Least One Medical History Term	xx (xx.x%)	xx	xx (xx.x%)	xx	xx (xx.x%)	xx
System Organ Class Preferred Term	xx (xx.x%)	xx	xx (xx.x%)	xx	xx (xx.x%)	xx

^a Counts reflect number of subjects reporting one or more medical history terms that map to MedDRA. At each level of summarization (System Organ Class or Preferred Term) subjects are counted once. Percentages are based on the number of subjects in the safety population.

^b Counts reflect number of medical history terms that map to MedDRA.

Note: MedDRA Version 21.0

SOURCE: USERNAME\SPONSOR\PROJECT\JOBNAME (DATE,TIME)

{NOTE TO PROGRAMMER: The table will be sorted by overall descending frequency of SOC and then, within a SOC, by overall descending frequency of PT}

Repeat Table 14.1.3.1 for the following table:

Table 14.1.3.2: Summary of Medical History by System Organ Class and Preferred Term (Per-Protocol Population)

Table 14.1.3.3: Summary of Medical History by System Organ Class and Preferred Term (Safety Population)

Table 14.1.4.1: Summary of Prior Medications by ATC Level 2 and Preferred Name
(Safety Population)
(Page 1 of xx)

ATC Level 2 Term ^a Preferred Name	E-BPO/E-ATRA 3%/0.1% Cream (N=xxx)	Vehicle Cream (N=xxx)
Number (%) of Subjects Reporting at Least One Prior Medication	xx (xx.x%)	xx (xx.x%)
ATC Level 2 Term	xx (xx.x%)	xx (xx.x%)
Preferred Name	xx (xx.x%)	xx (xx.x%)

^a Counts reflect number of subjects reporting one or more medications that map to the WHO term. At each level of summarization (ATC Level 2 Term or Preferred Name) subjects are counted once. Percentages are based on the number of subjects in the safety population.

Note: WHO Drug Global Dictionary, Format B3, Version March 1, 2018
Prior medications are those used before the date of first study drug application.

SOURCE: USERNAME\SPONSOR\PROJECT\JOBNAME (DATE,TIME)

Table 14.1.4.2: Summary of Concomitant Medications by ATC Level 2 and Preferred Name
(Safety Population)
(Page 1 of xx)

ATC Level 2 Term ^a Preferred Name	E-BPO/E-ATRA 3%/0.1% Cream (N=xxx)	Vehicle Cream (N=xxx)
Number (%) of Subjects Reporting at Least One Concomitant Medication	xx (xx.x%)	xx (xx.x%)
ATC Level 2 Term	xx (xx.x%)	xx (xx.x%)
Preferred Name	xx (xx.x%)	xx (xx.x%)

^a Counts reflect number of subjects reporting one or more medications that map to the WHO term. At each level of summarization (ATC Level 2 Term or Preferred Name) subjects are counted once. Percentages are based on the number of subjects in the safety population.

Note: WHO Drug Global Dictionary, Format B3, Version March 1, 2018
Concomitant medications are those used on/after the date of first study drug application.

SOURCE: USERNAME\SPONSOR\PROJECT\JOBNAME (DATE,TIME)

Table 14.2.1.1: Pooling Analysis for Primacy Efficacy Endpoints
(Intent-to-Treat Population)

Endpoint	Investigational Site Pooling Analysis		Analysis Center Pooling Analysis	
	Skewness P-Value	Investigational Site by Treatment Group P-Value	Skewness P-Value	Analysis Center Treatment Group P-Value
Absolute Change from Baseline in Inflammatory Lesion Counts at Week 12	x.xxx ^c		x.xxx ^c	
Ranked Analysis		x.xxx ^a		x.xxx ^c
Unranked Analysis		x.xxx ^b		x.xxx ^f
Absolute Change from Baseline in Non-Inflammatory Lesion Counts at Week 12	x.xxx ^c		x.xxx ^c	
Ranked Analysis		x.xxx ^a		x.xxx ^c
Unranked Analysis		x.xxx ^b		x.xxx ^f
Two Grade Reduction from Baseline in IGA and Achieving Clear or Almost Clear at Week 12	NA	x.xxx ^d	NA	x.xxx ^g

^a P-value for the interaction term from a ranked analysis of covariance with factors of treatment, investigational site, treatment by investigational site interaction and the respective Baseline lesion count as a covariate.

^b P-value for the interaction term from an unranked analysis of covariance with factors of treatment, investigational site, treatment by investigational site interaction and the respective Baseline lesion count as a covariate.

^c Skewness test, based on methods presented by J.H. Zar (1984), assessed for each imputed dataset. The average p-value is presented.

^d P-value for the interaction term from a logistic regression with factors of treatment, investigational site, treatment by investigational site interaction.

^e P-value for the interaction term from a ranked analysis of covariance with factors of treatment, analysis center, treatment by analysis center interaction and the respective Baseline lesion count as a covariate.

^f P-value for the interaction term from an unranked analysis of covariance with factors of treatment, analysis center, treatment by analysis center interaction and the respective Baseline lesion count as a covariate.

^g P-value for the interaction term from a logistic regression with factors of treatment, analysis center, treatment by analysis center interaction.

Note: Multiple imputation (MCMC) used to impute missing values.

SOURCE: USERNAME\SPONSOR\PROJECT\JOBNAME (DATE,TIME)

{NOTE TO PROGRAMMER: ADJUST FOOTNOTE “d” AND/OR “g” IF FIRTH’S PENALIZED LIKELIHOOD IS NEEDED}

Table 14.2.1.2: Primary Efficacy Analysis: Absolute Change from Baseline in Lesion Counts and Dichotomized IGA Success at Week 12
(Intent-to-Treat Population)

	E-BPO/E-ATRA 3%/0.1% Cream (N=xxx)	Vehicle Cream (N=xxx)	Skewness P-Value	Treatment P-Value
Inflammatory Lesion Count – Absolute Change from Baseline				
LSMean ^a	xx.x	xx.x	x.xxx ^b	x.xxx ^a
LSSD ^a	xx.xx	xx.xx		x.xxx ^c
Non-Inflammatory Lesion Count – Absolute Change from Baseline				
LSMean ^a	xx.x	xx.x	x.xxx ^b	x.xxx ^a
LSSD ^a	xx.xx	xx.xx		x.xxx ^c
At Least Two Grade Reduction from Baseline and Achieving Clear or Almost Clear				
Success	xx.x%	xx.x%	N/A	x.xxx ^d
Failure	xx.x%	xx.x%		

^a Least squares means, standard deviations and treatment p-value from an analysis of covariance with factors of treatment group and analysis center and the respective Baseline lesion count as a covariate. Negative least squares means values represent decrease from Baseline.

^b Skewness test, based on methods presented by J.H. Zar (1984), assessed for each imputed dataset. The average p-value is presented.

^c P-value from a ranked analysis of covariance with factors of treatment group and analysis center and the respective Baseline lesion count as a covariate.

^d P-value from a logistic regression with factors of treatment group and analysis center.

Note: Multiple imputation (MCMC) used to impute missing values.

SOURCE: USERNAME/SPONSOR/PROJECTJOBNAME (DATE, TIME)

{NOTE TO PROGRAMMER: ADJUST FOOTNOTE “d” IF FIRTH’S PENALIZED LIKELIHOOD IS NEEDED}

Repeat Table 14.2.1.2 for the following table:

Table 14.2.1.3: Primary Efficacy Analysis: Absolute Change from Baseline in Lesion Counts and Dichotomized IGA Success at Week 12 (Per-Protocol Population)

Update footnote to “Note: Missing values imputed using last observation carried forward.”

Table 14.2.2.1.1: Summary of Inflammatory Lesion Counts at Each Evaluation
(Intent-to-Treat Population)
(Page 1 of 4)

Inflammatory Lesion Counts	E-BPO/E-ATRA 3%/0.1% Cream (N=xxx)	Vehicle Cream (N=xxx)
Baseline		
n	xx	xx
Mean	xx.x	xx.x
SD	xx.xx	xx.xx
Median	xx.x	xx.x
Min. to Max.	xx to xx	xx to xx
Week 2		
n	xx	xx
Mean	xx.x	xx.x
SD	xx.xx	xx.xx
Median	xx.x	xx.x
Min. to Max.	xx to xx	xx to xx
Change from Baseline		
n	xx	xx
Mean	xx.x	xx.x
SD	xx.xx	xx.xx
Median	xx.x	xx.x
Min. to Max.	xx to xx	xx to xx
Percent Change from Baseline		
n	xx	xx
Mean	xx.x	xx.x
SD	xx.xx	xx.xx
Median	xx.x	xx.x
Min. to Max.	xx to xx	xx to xx

Note: Multiple imputation (MCMC) used to impute missing values. Summary statistics for Weeks 2, 4, 8, and 12 represent average values, obtained from averaging the summary statistics generated from each imputed dataset.

SOURCE: USERNAME\SPONSOR\PROJECT\JOBNAME (DATE,TIME)

Table 14.2.2.1.1: Summary of Inflammatory Lesion Counts at Each Evaluation
(Intent-to-Treat Population)
(Page 2 of 4)

Inflammatory Lesion Counts	E-BPO/E-ATRA 3%/0.1% Cream (N=xxx)	Vehicle Cream (N=xxx)
Week 4		
n	xx	xx
Mean	xx.x	xx.x
SD	xx.xx	xx.xx
Median	xx.x	xx.x
Min. to Max.	xx to xx	xx to xx
Change from Baseline		
n	xx	xx
Mean	xx.x	xx.x
SD	xx.xx	xx.xx
Median	xx.x	xx.x
Min. to Max.	xx to xx	xx to xx
Percent Change from Baseline		
n	xx	xx
Mean	xx.x	xx.x
SD	xx.xx	xx.xx
Median	xx.x	xx.x
Min. to Max.	xx to xx	xx to xx

Note: Multiple imputation (MCMC) used to impute missing values. Summary statistics for Weeks 2, 4, 8, and 12 represent average values, obtained from averaging the summary statistics generated from each imputed dataset.

SOURCE: USERNAME/SPONSOR/PROJECT/JOBNAME (DATE,TIME)

Table 14.2.2.1.1: Summary of Inflammatory Lesion Counts at Each Evaluation
(Intent-to-Treat Population)
(Page 3 of 4)

Inflammatory Lesion Counts	E-BPO/E-ATRA 3%/0.1% Cream (N=xxx)	Vehicle Cream (N=xxx)
Week 8		
n	xx	xx
Mean	xx.x	xx.x
SD	xx.xx	xx.xx
Median	xx.x	xx.x
Min. to Max.	xx to xx	xx to xx
Change from Baseline		
n	xx	xx
Mean	xx.x	xx.x
SD	xx.xx	xx.xx
Median	xx.x	xx.x
Min. to Max.	xx to xx	xx to xx
Percent Change from Baseline		
n	xx	xx
Mean	xx.x	xx.x
SD	xx.xx	xx.xx
Median	xx.x	xx.x
Min. to Max.	xx to xx	xx to xx

Note: Multiple imputation (MCMC) used to impute missing values. Summary statistics for Weeks 2, 4, 8, and 12 represent average values, obtained from averaging the summary statistics generated from each imputed dataset.

SOURCE: USERNAME/SPONSOR/PROJECT\JOBNAME (DATE,TIME)

Table 14.2.2.1.1: Summary of Inflammatory Lesion Counts at Each Evaluation
(Intent-to-Treat Population)
(Page 4 of 4)

Inflammatory Lesion Counts	E-BPO/E-ATRA 3%/0.1% Cream (N=xxx)	Vehicle Cream (N=xxx)
Week 12		
n	xx	xx
Mean	xx.x	xx.x
SD	xx.xx	xx.xx
Median	xx.x	xx.x
Min. to Max.	xx to xx	xx to xx
 Change from Baseline		
n	xx	xx
Mean	xx.x	xx.x
SD	xx.xx	xx.xx
Median	xx.x	xx.x
Min. to Max.	xx to xx	xx to xx
 Percent Change from Baseline		
n	xx	xx
Mean	xx.x	xx.x
SD	xx.xx	xx.xx
Median	xx.x	xx.x
Min. to Max.	xx to xx	xx to xx

